13.2.2 Relationship to IMP

Assessment of causality is based on the following considerations: associative connections (time and/or place), pharmacological explanations, previous knowledge of the drug, presence of characteristic clinical or pathological phenomena, exclusion of other causes, and/or absence of alternative explanations.

The Investigator will be asked to assess causal relationship to the trial treatment according to the following classifications:

- *Probably related*: An AE with a reasonable time sequence to administration of the IMP, unlikely to be attributed to concurrent disease or other drugs or chemicals, and which follows a clinically reasonable response on withdrawal (de-challenge). Re-challenge information is not required to fulfil this definition.
- *Possibly related*: An AE with a reasonable time sequence to administration of the IMP, but which could also be explained by concurrent disease or other drugs or chemicals. Information on drug withdrawal may be lacking or unclear.
- *Unlikely related*: An AE with a temporal relationship to IMP administration which makes a causal relationship improbable, and in which other drugs, chemicals or underlying disease provide plausible explanations.
- *Not applicable*: This assessment can be used e.g. in cases where the subject did not receive any treatment with IMP.

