10.1.1 Considerations Due to the COVID-19 Pandemic

Due to the COVID-19 pandemic, adjustments to the visit location/method or schedule may be made to accommodate safety concerns and restrictions experienced by individual subjects and sites. In all cases, subjects will be kept informed, via the site staff, as much as possible, of changes to the study and monitoring plans that could impact them.

Discontinuation of subjects from the study post-treatment with AMT-060 is not considered to be in the best interest of the subject, due to the irreversible nature of the IMP. Wherever possible, every effort is to be made to have the subject visit the clinic for the study visits according to schedule. Should a clinic visit not be possible, options that may be considered include site nurses travelling to a subject's home, local laboratory use, or home nursing services (for certain visits, if pre-approved by the Investigator and uniQure). These options, if used, will be supplemented with a phone call or telemedicine/telehealth safety follow-up call. A (temporary) transfer of a subject to an alternate clinical trial sites may also be considered in order to continue on-site visits, only if this does not pose undue burden to the subject and/or "new" site.

In some instances, it may not be possible to conduct any type of visit at all. Where none of the above options are feasible, subject visits may be moved beyond the maximum visit window permitted. Such delays will be assessed on a case by case basis. Until visits are rescheduled, supplemental phone calls or telemedicine/telehealth contact between Investigator/study staff and subject are to be arranged.

Supplemental phone calls or telemedicine/telehealth safety follow-up calls will be used to confirm the subject's status and wellbeing. At these calls, safety information should be gathered (i.e. AEs, concomitant medication use), subjects should be asked about any new unreported bleeds or FIX consumption and confirm their use of the e-diary (as applicable), and there should be continued discussions with the subject on the importance of a healthy liver. These discussions will be documented in the source documents.

All deviations from the study protocol are to be documented, with rationale. If a protocol deviation is due to the COVID-19 pandemic, this will be noted.

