11.2 IMP Administration

11.2.1 Dose Levels and Allocation to Dosing

Subjects will be allocated to the cohorts with the following planned dose levels based on the chronological order the subjects complete the screening visit (Visit 1):

- Cohort 1 (5 subjects): AAV5-hFIX 5×10^{12} gc/kg
- Cohort 2 (5 subjects): AAV5-hFIX 2×10^{13} gc/kg

Dosing will take place once (at Visit 2). No other medication will be provided in the trial.

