# 4.5.1 Adverse Events – Primary Safety Endpoint

All reported adverse events will be coded using the Medical Dictionary for Regulatory Activities (MedDRA version 17.1).

An AE is considered related with the use of drug if the relationship to IMP is classified as either 'Probably related' or 'Possibly related'. A related AE is referred to as an Adverse Drug Reaction (ADR).

An adverse event is defined as treatment emergent (TEAE) when onset of the event is after the administration of the IMP. In case an AE starts the same day of IMP administration and the exact time is missing, it will be defined as Treatment Emergent AE.

Adverse events for special notification are determined through the eCRF.

In case of missing or incomplete onset dates of AEs the onset date will be imputed such that the event starts as early as possible based on the partial date. Furthermore, if the AE could be treatment emergent based on the missing or incomplete date, then the AE will be regarded as treatment emergent.

Furthermore, missing values for AEs will be treated as missing except for causality and intensity. If causality is missing for a TEAE, the TEAE will be regarded as 'Probably related'. If causality is missing for an AE with onset before administration of trial drug, the AE will be regarded as 'Unlikely related'. If the intensity is missing the intensity of the AE will be regarded as severe. In case seriousness is missing this should be queried again since seriousness cannot be imputed as 'Yes' by default, since this would affect the reconciliation between trial data base and registry of SAEs.

All TEAEs will be tabulated, while pre-treatment AEs will only be listed.

An AE overview summary table will be prepared including the number of patients reporting at least one AE, the percentage of patients (%) with at least one AE, and the number of events (E) reported, for the following categories:

- TEAEs
- Related TEAEs
- Deaths
- Serious TEAEs
- Severe/Moderate/Mild TEAEs
- TEAEs leading to discontinuation of study treatment (defined as action taken='Drug withdrawn' on the AE form)
- TEAEs qualifying for special notification

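### The *Probably related* class requires a response on withdrawal, which cannot be observed for adverse events arising after a single irreversible infusion, so the Probably/Possibly split in Table 14.3.1.1 is not interpretable

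*Protocol*

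**What the plan says.** Protocol Section 13.2.2 asks the investigator to place each AE in one of four classes.

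- *Probably related*: reasonable timing, and the AE is "unlikely to be attributed to concurrent disease or other drugs or chemicals, and which follows a clinically reasonable response on withdrawal (de-challenge"). The next sentence adds: "Re-challenge information is not required to fulfil this definition". No such waiver is given for de-challenge.
- *Possibly related*: reasonable timing, "but which could also be explained by concurrent disease or other drugs or chemicals". Here, "Information on drug withdrawal may be lacking or unclear".
- *Unlikely related*: a causal relationship is improbable, and it is a case "in which other drugs, chemicals or underlying disease provide plausible explanations".
- *Not applicable*: the example given is a subject who never received the IMP.

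On exposure, Section 11.2.1 says "Dosing will take place once (at Visit 2"), and Section 10.1.1 advises against discontinuing treated subjects "due to the irreversible nature of the IMP".

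SAP Section 4.5.1 counts an AE as related if it is *Probably* or *Possibly related*. For gaps it says: "If causality is missing for a TEAE, the TEAE will be regarded as 'Probably related". The shell for Table 14.3.1.1 shows Probably, Possibly and Unlikely related events in separate rows.

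**The concern.** The scale is worded for a drug that can be stopped. In *Probably related*, the withdrawal condition is joined to the others by a plain conjunction and only re-challenge is excused. After a single infusion of a vector meant to give lasting expression, there is nothing to withdraw. The event with the strongest case for causation (right timing, nothing else to explain it) is therefore the one the scale cannot place.

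The protocol expects such events. Section 11.2.3 discusses an ALT rise without another aetiology, and Section 13.1 defines an adverse drug reaction by a reasonable possibility of causation. Such a rise could be a drug reaction under 13.1 and still have no class under 13.2.2.

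AEs are the primary endpoint. If sites improvise differently, the grading of relatedness in the primary safety tables reflects each site's workaround. If any site resolves the gap by choosing *Unlikely*, a vector-related event drops out of the related count.

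**Working it through.** No figure in the plan is at issue, so the check applies the definitions in Section 13.2.2 to four kinds of AE in a dosed subject with reasonable timing.

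| AE | Probably | Possibly | Unlikely | Not applicable |
|---|---|---|---|---|
| A. After infusion, no plausible alternative cause | Fails: no de-challenge | Fails: no other explanation | Fails: causation not improbable, no other explanation | Does not fit: subject was dosed |
| B. After infusion, alternative unlikely but not excluded | Fails: no de-challenge | Can fit | Fails unless causation is improbable | Does not fit |
| C. After infusion, credible alternative cause | Fails: alternative is credible, no de-challenge | Fits | Only if causation is improbable | Does not fit |
| D. During infusion, no alternative, subsides on interruption | Can fit | Fails: no other explanation | Fails | Does not fit |

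Type A fits 0 of 4 classes, and 0 of the 2 related classes. No post-infusion type (A, B or C) reaches *Probably related*. With the de-challenge condition removed, type A fits *Probably related*: 1 class instead of 0.

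Next, where the class is used:

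| Use | Probably and Possibly |
|---|---|
| SAP 4.5.1 definition of a related AE; Table 14.3.1.3 | Pooled |
| Protocol 19.2.1, stopping rules 2 and 4 | Pooled; recruitment period only |
| Protocol 13.7, follow-up of severe non-serious AEs still ongoing after participation ends | Pooled |
| SAP Table 14.3.1.1 | Separate rows |

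A type A event recorded as *Possibly* instead of *Probably* changes only the last line. A type A event recorded as *Unlikely* changes all four.

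If investigators obeyed the definition exactly, the Probably row could hold only two kinds of record: TEAEs with missing causality, imputed under SAP 4.5.1, and any infusion reaction of type D. Neither is what a reader of that row would expect.

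Scale: Section 9.1 plans 5 subjects per cohort, with up to 2 more in Cohort 2. One subject whose only event in a row moves elsewhere changes that row by 1/5 = 20 percentage points in a cohort of 5, or 1/7 = 14.3 points in a cohort of 7.

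**The case against.** The strongest reply is that the scale is graded and used with judgement. Section 13.2.2 opens by naming the exclusion of other causes and the lack of alternative explanations among the considerations for causality, which points an assessor towards *related* for a type A event. *Possibly* needs only that something else could explain the AE, and it tolerates missing withdrawal information, so many events will fit there. The shell for Table 14.3.1.3 already lists liver enzyme terms under related TEAEs. Shells hold no results, but this suggests such events were expected to be classed as related.

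Most of this stands, and it limits the consequences. It does not repair the definition: the investigator must still choose one of the classes as worded, and the opening considerations do not remove a stated condition from one of them.

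A reader might infer three stronger things that the documents do not support.

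- That no AE at all can be *Probably related*. A reaction during the infusion could subside on interruption. Infusion start and stop times are recorded (Table 5-3), and AEs related to the administration procedure are specially notified (Section 13.6).
- That the safety stopping rules fail. Rules 2 and 4 pool the two classes. Rule 1, on ALT and AST, has no relatedness condition. Section 19.2.1 limits all the rules to recruitment, which had ended by the 52-week interim analysis (cut-off 12 May 2017, SAP Appendix 1).
- That liver, inhibitor or cancer events could be missed. Section 13.6 requires special notification of transaminase elevation above 1.5 times baseline, confirmed FIX inhibitors, thromboembolic events and new or recurrent cancer, with no causality condition on those items.

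**Conclusion.** The definition is wrong as written for this product. No text in the Protocol, SAP or DMC charter adapts the de-challenge condition to a single infusion. AEs arising after the infusion cannot literally be *Probably related*, and those with no plausible alternative cause have no valid class.

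The main effect is that the separate Probably and Possibly rows of Table 14.3.1.1 cannot be interpreted. No decision rule in the documents uses that split. A smaller risk is that a clearly vector-related AE is placed outside the related classes. Only in that case do the pooled related count, stopping rules 2 and 4 (during recruitment) and the Section 13.7 follow-up change.

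This rests on reading the conditions of *Probably related* as jointly required, and on the end of a one-off infusion not being a withdrawal. How investigators actually classified events is not in the documents, so the number affected cannot be given.

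**What to change.** In Section 13.2.2, delete the de-challenge condition from *Probably related*, or limit it to cases where it applies. Add that neither de-challenge nor re-challenge information is required for this single-infusion IMP. The remark on withdrawal information under *Possibly related* does no harm and can stay.

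For AEs already assessed, do not re-query causality only for events that could move upward. In an open-label trial that would push the result in one direction. Do not alter the 52-week data, which Section 20.1 treats as locked. Report the pooled Probably/Possibly category as the interpretable one. SAP 4.5.1 already lists related TEAEs as a single category for the overview table, so a pooled row in Table 14.3.1.1 would match its text. State in the SAP and the CSR that the split was collected under the wording with the de-challenge condition.

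The cost is a short protocol amendment, one added table row and a sentence each in the SAP and CSR. The downside is that the Probably/Possibly split will not be comparable before and after the change. No dose or clinical rule is affected.

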13.2.3 Outcome

The Investigator will be asked to record the most appropriate outcome of the following:

- Recovered
- Recovered with sequelae
- Recovering
- Not recovered
- Fatal
- Unknown

Clinical Trial Protocol

Trial ID: CT-AMT-060-01

13.3 Reporting of Adverse Events

All events meeting the definition of an AE must be reported in the period starting at the first visit during which any trial related activity takes place until the end of trial participation. At each visit the subject will be asked about AEs in an objective manner, e.g.: “Have you experienced any problems since the last visit?”. Only medically qualified personnel (Investigators) must assess AEs.

AEs must be reported in the source data and the eCRF. The diagnosis will be recorded, if available and applicable. If no diagnosis is available each sign and symptom will be recorded as individual AEs.

Recurring AEs should be reported separately, i.e. with separate start date and time and stop date and time.

13.4 Prompt Reporting of SAEs and Other Events to uniQure

SAEs, AEs qualifying for special notification and disease-related bleeding episodes related to the IMP and/or with fatal outcome, must be reported as described in the following table once the Investigator determines that the event meets the protocol definition for that event.

Type of Event	Initial Reports		Follow-up Information on a Previous Report	
	Time Frame	Documents	Time Frame	Documents
All SAEs	24 hours	SAE form	72 hours*	SAE form
All AEs qualifying for special notification as defined in Section 13.6	24 hours	SAE form	72 hours*	SAE form
Disease-related bleeding episodes related to the IMP and/or with fatal outcome as defined in Section 13.8	24 hours	SAE form	72 hours*	SAE form

* If however, in the opinion of the Investigator, the follow-up information may have implications for the safety of other subjects, the follow-up information is to be reported immediately (i.e. within 24 hours).

The information will be reported on a paper SAE form and will include assessment of severity, causal relationship to the IMP or trial procedures, action taken, outcome, and a narrative description of the course of the event. Additional information may be subsequently provided.

The paper SAE form and all other relevant documents supporting the reported SAE or AE qualifying for special notification (e.g. diagnostic procedures, hospital records, autopsy reports) must be faxed or scanned/e-mailed to

CCI
24 hour Hotline: PPD
F: PPD
E-mail: PPD

Clinical Trial Protocol

Trial ID: CT-AMT-060-01

uniQure

The Independent Ethics Committees/Institutional Review Boards (IECs/IRBs) and regulatory authorities will be notified of SAEs according to current regulation and local requirements.

SAEs occurring to a subject after the subject has completed the clinical trial and for which a reasonable possibility of a causal relationship is assessed by the Investigator, should be reported by the Investigator to the sponsor if the Investigator becomes aware of them regardless of the time that has elapsed (post-trial events).

13.5 Regulatory Reporting Requirements for SAEs and Other Events

Prompt notification by the Investigator to uniQure of SAEs, AEs qualifying for special notification and disease-related bleeding episodes related to the IMP and/or with fatal outcome is essential, so that legal obligations and ethical responsibilities towards the safety of subjects are met.

uniQure has a legal responsibility to notify both the local regulatory authority and other regulatory agencies about the safety of a product under clinical investigation. uniQure will comply with ICH/Food and Drug Administration (FDA)/European Medicines Agency (EMA) and country-specific regulatory requirements relating to safety reporting to the regulatory authority, IECs/IRBs and Investigators. Details are laid down in the safety reporting plan which will comply with these regulatory requirements (e.g. 21CFR 312.32).

Expedited reporting of suspected unexpected serious adverse reactions will be taking place within 7 or 15 days depending on fatal/life threatening status, seriousness, expectedness and causality from all clinical trials globally (suspected unexpected serious adverse reaction [SUSAR] reporting in EU and IND safety reports in the US). Any suspected adverse reaction that is both serious and unexpected according to the Investigator's Brochure will be reported provided there is evidence to suggest a causal relationship between the drug and the AE.

Relevant follow-up information to an SAE IND safety report will be submitted as soon as the information is available.

Information about SUSARs is also forwarded to Investigators and IECs/IRBs as necessary.

An Investigator who receives an SUSAR describing an SAE(s) or other specific safety information (e.g. summary or listing of SAEs) from uniQure will file it with the Investigator's Brochure and will notify the IEC/IRB, if appropriate according to local requirements.

In addition to submission of SAEs, an annual Development Safety Update Report (DSUR) will be prepared and submitted to the EMA, FDA, and locally if applicable according to the development international birth date (DIBD).

13.6 Adverse Events Qualifying for Special Notification

New AEs potentially related to the conduct of the trial or the development of the Advanced Therapy Medicinal Products (ATMP) and likely to affect the safety of the subjects should be

Clinical Trial Protocol

Trial ID: CT-AMT-060-01

uniQure

reported and followed in the same manner as SAEs (see [Section 13.3](#) and [Section 13.7](#)). Note that the AEs may be serious or non-serious by definition (see [Section 13.1](#)).

In addition, the following (S)AEs qualify for special notification as they are seen as safety issues of particular concern for ATMPs ([ENTR/F/2/SF/dn D\(2009\) 35810. Brussels, 03/12/2009](#)) and gene therapy medicinal products ([EMEA/CHMP/GTWP/60436/2007](#)):

- AEs related to the IMP administration procedure (intravenous infusion)
- Suspected or confirmed cases of opportunistic or serious infections that in the Investigator's opinion might be related to the IMP
- Unexpected reactions (e.g. hypersensitivity, immunological, toxic or other as consequence of a change in the construction or function of the viral vector [e.g. generation of replication competent virus])
- AEs related to product failure (including lack of efficacy)
- Confirmed FIX inhibitors
- Thromboembolic events
- Transaminase elevation > 1.5 times baseline value
- Allergic reactions
- AEs that could be related to potential off-target expression
- Development of any new/recurrent cancer.

13.7 Follow-up on Adverse Events

All AEs should be followed until they have reached a "final outcome" (recovered, recovered with sequelae, recovering, not recovered, fatal or unknown) or the subject's participation in the trial ends, whichever comes first.

Severe, non-serious AEs assessed as "Probably related" or "Possibly related" to IMP and all SAEs and AEs qualifying for special notification (regardless of their relationship to IMP) still ongoing after ended trial participation, should be followed on a regular basis according to the Investigator's clinical judgment until a "final outcome" has been established.

The outcome "recovering" can be used as the "final outcome" for events that are stabilized (i.e. no further worsening is expected) and expected by the Investigator to resolve over time.

The outcome "not recovered" can be used as the "final outcome" for events that are not expected to resolve over time (e.g. cancer).

If a subject dies during the reporting period attempts should be made to obtain biopsy material to perform assay for replication competent retrovirus or other relevant part of the gene therapy medical product and to ascertain the cause of the death ([EMEA/CHMP/GTWP/60436/2007](#)).

13.8 Reporting Requirements for Disease-Related Bleeding Episodes

Disease-related bleeding episodes evaluated by the Investigator as part of the underlying disease should not be reported as AEs unless related to the IMP (including bleeding episodes due to lack of efficacy of the IMP) or if the bleeding has worsened as compared to the subject's normal bleeding pattern, as evaluated by the Investigator. In case a bleeding episode

Clinical Trial Protocol

Trial ID: CT-AMT-060-01

uniQure

is meeting one or more of the SAE criteria or is related to major surgery requiring in-patient hospitalization, it must be reported as an SAE.

13.9 Pregnancies

Pregnancies of the subject's sexual partner will be recorded separately from AEs, but will be reported in a manner identical to the reporting of SAEs, however via the use of a pregnancy reporting form instead of a SAE form.

All attempts will be made to record all pregnancies occurring during this trial for which the subject received IMP and where the subject's sexual partner has become pregnant after IMP administration.

All attempts will be made to follow-up the pregnancy until the outcome of the pregnancy has been determined and to capture information on the development of the infant in the period up until and including the age of 1 year. This information will only be collected if separate informed consent is given by the subject and the subject's sexual partner.

Any report of a congenital abnormality/birth defect is an SAE and should be reported as such. Any complication of a pregnancy occurring during this trial, including elective termination for medical reasons, must be reported with the pregnancy reporting form.

